d. Protocol and Measurements. Visit 1: Health, lifestyle and sleep questionnaires (i.e. SF-36 Health survey and Epworth Sleepiness Scale) along with pulmonary function tests, blood pressure measurements, a 12-lead electrocardiogram and a physical examination will be completed. Visit 2: A sleep study beginning at approximately 10 pm will be completed. The study will be used to confirm the presence or absence of OSA. Visit 3: A sleep study will be completed to determine the therapeutic positive airway pressure required to eliminate flow limitation. In addition, the pressure associated with airway collapsibility will be determined (i.e. the critical closing pressure - PC_{CRIT}). Upon awakening participants in Hypoxia group will undergo a trial exposure to IH (two 2-minute episodes of 8% oxygen separated by two-minute normoxic intervals, with an accompanied 2 mmHg increase in carbon dioxide levels) while sham group will be exposed to room air in order to acclimate to the equipment and accompanying sensations. Visit 4: Following the sleep study, participants will be given a blood pressure holter monitor (ABPM-05, Meditech Inc. Framingham, MA) to measure blood pressure and pulse rate at home over a 24-hour period. Data collection will begin at 6 am on a weekend day. Blood pressure values will be obtained every 20 minutes. Participants will be given a diary and an actigraph watch to document activities completed over the 24-hour period. Thereafter data will be standardized relative to activity level (i.e. quiet and active wakefulness and sleep). Participants will be encouraged to adhere to a daily routine that will be replicated following completion of the IH protocol. These measures are being made to monitor the changes in blood pressure associated with activities of daily living. Visits 5 - 19: Following the completion of visits 1-4, participants will visit the lab 15 times over a 3-week period during the day. The participants will visit the laboratory each week day for 3 weeks. If a week day visit is missed it will be replaced by a visit on a week end day. During each visit, participants in Hypoxia group will be exposed to 12 two-minute episodes of 8% oxygen combined with a 2 mmHg increase in carbon dioxide separated by two minute normoxic intervals. The IH protocol will be comprised of a 20-minute baseline period followed by exposure to twelve - two minute episodes of hypoxia [partial pressure of end-tidal oxygen (PETO₂) = 50 mmHg]. Each episode will be interspersed with a 2-minute recovery period under normoxic conditions. The PETCO₂ will be sustained 2 mmHg above baseline values for the last ten minutes of baseline and throughout the remainder of the protocol. In addition to the IH protocol, a group of participants will also be exposed to a sham protocol in addition to being treated with CPAP during sleep. The sham protocol will be administered during wakefulness for a minimum of 15 days over a 3-week period. During the sham protocol the participants will be exposed to atmospheric levels of oxygen and carbon dioxide for the duration of the IH protocol. During the IH and sham protocol respiratory

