Research staff that will not administer the gases will be assigned to complete a blind analysis of all measures. The staff assigned to analyze data (e.g. ventilation and blood pressure) collected during the direct application of hypoxia might be able to determine the applied stimulus based on the respiratory or cardiovascular response. However, the criteria used to analyze the data is rigorous and bias is unlikely. The Shapiro-Wilk test will be used to test if the data is normally distributed. Assuming that the data will be normally distributed, a two-way analysis of variance with repeated measures in conjunction with Student-Newman Keuls post-hoc test will be used to determine if differences in 24 hour blood pressure measures are evident before and after exposure to IH or the sham protocol. The two factors in the design will “Group (Hypoxia vs. sham)” and “time point (Visit 4 vs. Visit 20).” A similar analysis will be used to determine if primary (i.e. blood pressure, autonomic nervous system activity, therapeutic CPAP, critical closing pressure, limb motor function tests) and secondary (vigilance and neurocognitive measures and blood biomarkers) outcome measures differ before, midway and after completion of the IH or sham protocol. The two factors in the design will be “Group (Hypoxia vs. sham)” and “time point (Visit 5 vs. Visit 12 vs. Visit 19)”. Primary outcome variables collected during IH or the sham protocol (i.e. blood pressure, autonomic nervous system activity, minute ventilation, tidal volume, breathing frequency, PETCO₂, PETO₂) will be analyzed using a three-way analysis of variance with repeated measures in conjunction with Student-Newman Keuls post hoc. The three factors in the design will be “Group (Hypoxia vs. sham)”, “Visit Number (Visit 5 vs. Visit 12 vs. Visit 19)” and “Time Point (Baseline vs. Initial hypoxic episode vs. Final hypoxic episode vs recovery of IH or sham protocol).” A Pearson product-moment correlation and regression analysis will be used to examine the relationship between CPAP adherence (e.g. percentage of days CPAP used over 4 or 6 hours) during the last half of the protocol with changes in the primary and secondary outcome measures for hypoxia and sham groups. If CPAP adherence impacts on the primary and/or secondary outcome measures we expect the slope of the relationship will be greater in Hypoxia group compared to sham group (i.e. for a given level of adherence modification to the primary or secondary outcome variable will be greater in the CPAP and IH group compared to the CPAP and sham group).

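### For the four-level within-session time factor, Student-Newman-Keuls lets the chance of at least one false difference reach about 9 to 9.75% in the Hypoxia group, for outcomes that respond clearly to the gas

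*Combined protocol and SAP*

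**What the plan says.** Data and Statistical Analysis states that the within-session outcomes will be "analyzed using a three-way analysis of variance with repeated measures in conjunction with Student-Newman Keuls post hoc". The factors are group, visit (three levels: 5, 12 and 19) and a four-level time factor within the session, whose levels are given as "Baseline vs. Initial hypoxic episode vs. Final hypoxic episode vs recovery of IH or sham protocol". The outcomes, all called primary, are "blood pressure, autonomic nervous system activity, minute ventilation, tidal volume, breathing frequency" and end-tidal carbon dioxide and oxygen: seven in all. The section gives no significance level, no family of comparisons, no named contrast and no other multiplicity control.

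Under Protocol and Measurements, the Hypoxia group is "exposed to 12 two-minute episodes of 8% oxygen combined with a 2 mmHg increase in carbon dioxide separated by two minute normoxic intervals", so the stimulus is nominally the same at the first and last episodes. End-tidal carbon dioxide "will be sustained 2 mmHg above baseline values for the last ten minutes of baseline and throughout the remainder of the protocol". The Sham group breathes atmospheric gas throughout. Participants sets each group at 4.

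**The concern.** Student-Newman-Keuls orders the means and tests the widest range first. It steps inward only while the ranges keep being rejected, and each range is compared with the 5% critical value for the number of means it spans. It therefore protects the family when all means are equal. It does not when four means form two separate pairs of equals: the wide ranges reject because the pairs really differ, and each pair is then tested as if it were the only one.

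This design can produce that pattern in the Hypoxia group. If an outcome responds strongly to hypoxia and nothing carries over, Initial equals Final, Baseline equals Recovery, and the two sets are far apart. The wide steps then show only that the gas worked. The two comparisons left are the scientifically interesting ones: whether the outcome stays changed after exposure, and whether the response grows across episodes. Student-Newman-Keuls is the only protection the plan names for them.

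**Working it through.** The plan gives no alpha, power or family-error figure, so there is nothing of its own to reproduce.

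**Inputs**
- Time points: 4. Visits: 3 (Data and Statistical Analysis).
- Participants: 4 per group, 8 in total (Participants).
- Error degrees of freedom: Hypoxia group alone at one visit, (4−1)×(4−1) = 9; time by subject within group, (4−1)×(8−2) = 18; three-way error term, (4−1)×(3−1)×(8−2) = 36.
- Assumed, because not stated: alpha 0.05 two-sided; the family is the pairwise comparisons of the four time points within one group, visit and outcome.
- Configuration: true means (0, D, D, 0) for Baseline, Initial, Final and Recovery, with D in error SDs and equal error variance.

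**Limit for well-separated pairs.** Once the wide ranges reject, each pair is tested at 5%. Treating the pairs as independent:

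1 − (1 − 0.05)² = 0.0975.

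The two pairs share one error estimate, which lowers this slightly. By simulation it is 9.4% (9 df), 9.6% (18 df) and 9.7% (36 df). At 18 df, 9.6/5 = 1.9 times the assumed level.

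**Full step-down, n = 4, simulated with 9, 18 and 36 df**

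| Gas effect D | At least one false difference |
|---|---|
| 0 (all means equal, as in Sham) | about 5% |
| 1 SD | 5.5–6.0% |
| 2 SD | 8.9–9.6% |
| 3 SD or more | 9.1–9.8% (simulation error included) |

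For well-separated pairs, Recovery vs Baseline alone is 5.0% and Final vs Initial alone is 5.0%. The excess is in the union of the two.

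**Fewer levels.** With three levels, at most one pair of equal means can remain once a third mean differs, so Student-Newman-Keuls holds 5%. With two levels there is one comparison. The Visit 5/12/19 and Visit 4/20 time analyses are therefore not affected.

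**Alternatives on the two-pair pattern (D of 2 SD or more)**
- Holm on the two named contrasts: an error needs the smaller p at or below 0.05/2 = 0.025, so the family error is at most 2×0.025 = 5%. Simulated: 4.6–5.3%.
- REGWQ: a pair out of four is tested at 1 − 0.95^(2/4) = 2.5%, so two pairs give 1 − 0.95 = 5%. Simulated: 4.7–5.0%.
- Tukey: 2.0–2.4%, which is safe but stricter than needed for two contrasts.

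**The case against.** The strongest objection is that the worst case is conditional. It needs both pairs to be truly null and a gas effect of about 2 error SD or more. That is secure for end-tidal oxygen, which is set by the gas and so says nothing about facilitation. It is likely for ventilation: Potential Problems & Solutions expects participants may notice faster breathing and heart rate. It is unproven for blood pressure and autonomic activity, and carbon dioxide is held constant. Recovery vs Baseline is not even a clean null if the first half of baseline is used, because carbon dioxide is raised only in its last ten minutes and the plan does not name the segment. All of this stands and limits the point. It does not restore control of the family error for the outcomes where the pattern arises.

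A reader might also infer more than the documents support:

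- *False claims of facilitation double.* The Specific Aim 1 rationale ties facilitation to upper airway muscle activity, which is not among the seven outcomes. The related measures, therapeutic pressure and critical closing pressure, are in the unaffected two-way analysis. If facilitation is read as Recovery above Baseline, that contrast is tested at 5% two-sided, about 2.5% in the upward direction. A false upward difference in either pair occurs only about 4.6–5.1% of the time.
- *The error is about a quarter over three visits.* Figures of 23–26% arise if each visit is read separately with no gate, which the plan does not commit to. Even one contrast at 5% per visit gives 1 − 0.95³ = 14%, so much of this is not due to Student-Newman-Keuls. Requiring a significant three-way interaction first brought the figure to 2.9% in simulation.
- *The error is 15–26% in a session.* This requires hypoxic-period SDs 1.5 to 3 times larger, together with a pooled error term. The ratio is an assumption that the documents do not inform, and the problem is one of unequal variance.

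**Conclusion.** The point holds in a limited form. Student-Newman-Keuls is the wrong post-hoc procedure for the four-level Time Point factor. In the Hypoxia group, for outcomes with a gas effect of about 2 error SD or more and two truly null pairs, the chance of at least one false difference per outcome and session is about 9 to 9.75%. The comparison level of 5% and the family are assumptions, because the plan states neither; the figures also assume equal error variance. At a gas effect of 1 SD the inflation is slight, and in the Sham group there is none.

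This is a moderate defect. Reading seven primary outcomes at three visits without adjustment is a larger source of error. It is still worth correcting, because the session design produces the configuration in which the procedure fails and the correction is only wording.

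**What to change.** In the three-way analysis:

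1. Replace Student-Newman-Keuls by Holm over two pre-named contrasts: Recovery minus Baseline, and Final minus Initial episode. If all pairs are wanted, use REGWQ.
2. Define Baseline for this contrast as its last ten minutes, where carbon dioxide is matched to the rest of the session.
3. State alpha, and whether the family is one visit (two contrasts) or all three (six contrasts).
4. Report hypoxic against non-hypoxic points only as a check that the gas worked.
5. Keep the ANOVA error term unless the variances clearly differ.

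**Cost.** With Holm over two contrasts, the smaller p must reach 0.025. At 18 df the critical t rises from 2.10 to about 2.45, so there will be somewhat fewer positive calls. With all six contrasts in one family, the smallest p must reach 0.05/6 = 0.0083.

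Contrast-specific error terms would guard against unequal variance, but they leave only 4 − 1 = 3 df in the Hypoxia group. The critical t is then 4.18 at 0.025 and 6.23 at 0.05/6, a large loss of power. They are not needed to cure this defect. Treat them as optional, and state the cost if they are chosen.

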Mild Intermittent Hypoxia and CPAP: A Multi-Pronged Approach to Treat Sleep
Apnea in Intact and Spinal Cord Injured Humans

Record # 1 R56HL142757-01

Date: November 5th 2018

Experimental Protocol

Specific Aim 1. To determine if IH coupled with CPAP mitigates autonomic, cardiovascular, neurocognitive and metabolic measures both directly and indirectly by improving CPAP compliance as a consequence of LTF of upper airway muscle activity initiated by exposure to IH.

a. Rationale. Many studies have reported that IH directly mitigates co-morbidities typically associated with OSA. In addition, exposure to IH may increase CPAP compliance by initiating LTF of upper airway muscle activity that could enhance upper airway patency leading to a reduction in therapeutic CPAP. Reduced pressures could result in improved compliance and outcome measure.

b. Recruitment. The participants with OSA may be recruited from Sleep Disorders Centers affiliated with Wayne State University and John D. Dingell Veterans Administration Medical Center. The total number of patients studied in these laboratories per year is approximately 4500 and about 40 % of the participants will meet the inclusion criteria. We will also target hypertension clinics at John D. Dingell VA Medical Center and the Detroit Medical Center as additional sites to recruit participants with coincident hypertension and OSA; since up to 30 % of individuals diagnosed with hypertension also have been diagnosed with OSA. Advertisements will also be placed in the local newspaper (i.e. Metro Times) and on various websites (i.e. Craigslist, Facebook and Wayne State University Pipeline). During recently completed studies approximately 100 individuals were screened in order to recruit 20 participants that met the inclusion criteria. In the present proposal we believe this rate of recruitment will improve because our inclusion criteria is less stringent than in the past (i.e. previously we recruited individuals with OSA that fell within a narrow age range and did not suffer from other co-morbid conditions). Based on past experience, once participants meet the inclusion criteria and have successfully completed the screening sleep study and practice trial few drop out beyond this point. Nonetheless we have taken into account that 2 participants from each group (see Participants below) may drop out beyond the point of the screening and practice trials, so an additional 4 participants may be enrolled if required.

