c. Participants. To complete the R56 proposal, Hypoxia group will be comprised of 4 participants with OSA that will be treated with IH and CPAP. Sham group will be comprised of 4 participants with OSA that will be exposed to a sham protocol and CPAP. Participants will be randomized to Hypoxia or Sham group. Participants will be male or female of any race, 18-60 years of age with a BMI of less than 40 kg/m² and pure or predominantly (i.e. comprised of both a central and obstructive component) OSA (AHI \leq 80 events per hour and an average oxygen desaturation level of 85 % or greater). Participants will not have received CPAP treatment previously. Participants' will be diagnosed with Stage 1 to Stage 2 hypertension as categorized by the 2018 American Heart Association guidelines. Systolic and diastolic pressure will range from 130 - 159 mmHg and 80 - 99 mmHg, respectively. Participants with a systolic pressure greater than 159 mmHg or a diastolic pressure greater than 99 mmHg will be excluded from the study. Based on the characteristics of this group the short exposure to mild IH that we will induce does not pose a risk beyond what exists for participants without OSA based on previous studies we have completed. Moreover, the nocturnal oxygen desaturation routinely experienced by the recruited participants will be mild, which will reduce the possibility of central nervous system hypoxic depression. Thus, we believe that initiation of various forms of plasticity following exposure to IH may manifest themselves more clearly in these individuals. The participants will be free of any other known cardiovascular disease. The participants will not be on any medications used to treat

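### The plan predicts a steeper adherence–outcome slope in the Hypoxia group but states no test or interval for the slope difference

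*Combined protocol and SAP*

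**What the plan says.** The Data and Statistical Analysis section states the method: "A Pearson product-moment correlation and regression analysis will be used to examine the relationship between CPAP adherence" in the last half of the protocol "with changes in the primary and secondary outcome measures for hypoxia and sham groups". Adherence is given by example as the "percentage of days CPAP used over 4 or 6 hours". The prediction follows: if adherence affects outcomes, "we expect the slope of the relationship will be greater in Hypoxia group compared to sham group". A parenthesis glosses this as a larger outcome change with IH than with sham at the same adherence.

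The section gives no regression terms, Group × adherence product, test of parallel slopes, interval or significance level for this analysis. The repeated-measures ANOVAs have their factors listed (group, visit number, time point), and adherence is not among them.

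On size, section c. Participants says "Hypoxia group will be comprised of 4 participants with OSA that will be treated with IH and CPAP" and "Sham group will be comprised of 4 participants with OSA that will be exposed to a sham protocol and CPAP". Section b. Recruitment allows that "2 participants from each group (see Participants below) may drop out beyond the point of the screening and practice trials" and provides for up to 4 further enrolments.

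**The concern.** The prediction is about a difference between two slopes. A correlation or slope estimated in one arm answers another question: whether adherence and outcome are related in that arm at all. With no stated test of the difference, whoever writes the report must choose how to judge the prediction after seeing the data. Two informal routes are open: see which slope estimate is larger, or see whether the association is significant in one arm and not in the other. Neither controls the chance of a false claim about the difference.

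This is the plan's only named statistical analysis linking adherence to outcome change, and Specific Aim 1 gives improved adherence as one of the two routes by which IH is meant to work. The analysis is repeated over all primary and secondary outcomes, so some apparent confirmations are to be expected by chance. At stake is a claim that IH makes a given amount of CPAP use more effective.

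**Working it through.** **Inputs from the documents.** 4 participants per arm; a directional prediction, Hypoxia slope greater than Sham slope; five primary measures or families listed for the before, midway and after comparison, plus the secondary measures. The documents give no significance level, slope, correlation or SD for this analysis, so there is no planned figure to reproduce.

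**Assumptions.** Normal adherence and normal errors with the same error SD in both arms; two-sided 5% level; outcomes signed so that the predicted direction is positive; true correlations from 0 to 0.9; 200,000 simulated trials per setting.

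**Route 1: compare the two slope estimates.** Write D = b(Hypoxia) − b(Sham). If the true slopes are equal and the errors are independent and symmetric, D is symmetric about 0, so P(D > 0) = 0.5. Sample size does not enter. Simulation gives 49.9–50.1% at 4 per arm and 49.9–50.2% at 6 per arm. Over five outcomes, 5 × 0.5 = 2.5 would be expected to point the predicted way with no slope difference, whether or not the outcomes are correlated. If they were independent, the chance of at least one is 1 − 0.5⁵ = 96.9%.

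If steeper means larger in absolute value, the figure moves when adherence spread differs. It is 57.4% with the Hypoxia adherence SD halved and 48.0% with it doubled (common slope of 1 error SD per Sham SD of adherence).

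**Route 2: significant in Hypoxia, not in Sham.** With n = 4 there are 2 df and the critical t is 4.303. The critical correlation is t/√(t² + n − 2) = 4.303/√(18.52 + 2) = 0.95. At zero true correlation the arms are independent, so the chance of the predicted pattern is 0.025 × 0.95 = 0.024. With equal true slopes, simulation gives:

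| True correlation in Sham | Equal adherence SDs | Hypoxia adherence SD halved |
|---|---|---|
| 0 | about 2% | – |
| 0.5 | 8% | – |
| 0.7 | 14% | 6% |
| 0.8 | 19% | 8% |
| 0.9 | 25% | 10% |

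The excess over 2.5% therefore needs a real adherence effect in both arms, and it shrinks if adherence varies less in Hypoxia.

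**Direct test of the difference.** Fit change = β0 + β1·Group + β2·adherence + β3·Group × adherence. The slope difference is β3, on 8 − 4 = 4 residual df (critical t 2.78). With equal true slopes the test rejects in 4.95–5.07% of trials, and in about 2.5% in favour of Hypoxia.

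**Power of that test.** For a Hypoxia slope 1.5 times the Sham slope, at Sham correlations of 0.7 to 0.9, it is 7–14% with equal adherence SDs and 6–9% with the Hypoxia SD halved. For a slope difference of 1 error SD per SD of adherence it is about 13%, and for a difference of 2 about 35%.

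**The case against.** The strongest reply is that the plan commits to none of this. The sentence is a conditional expectation and not a criterion for a claim. The regression is unspecified, so a pooled model with a product term may be what the investigators intend. Nothing says the arms are fitted separately. All of that stands. A reader might infer that the plan adopts a rule with a 50% false-positive rate; the documents do not support that. The 50% is what follows only if the direction of the estimates is taken as the evidence.

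A reader might also infer that correlation coefficients will be compared between arms, and would mislead if good adherence bunches near 100% in Hypoxia. The documents do not support this either: the prediction is about slopes, regression is planned beside correlation, and no adherence spread is given.

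A further reply is that 8 people cannot settle the question under any wording, and that treatment effects are assessed by the Group-by-time ANOVAs, which this point leaves alone. Both are true and limit its weight. They do not remove it: when power is this low, a wide interval shows that the question is open, whereas a bare comparison of estimates can look like confirmation.

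**Conclusion.** The point holds as a gap in specification. The plan predicts a between-arm slope difference and names no test or interval for it. If the prediction is judged from the arm-level estimates, equal true slopes show the predicted direction in 50% of comparisons; for the signed difference this rests only on symmetric errors. If it is judged by significance in Hypoxia alone, the rate at 4 per arm runs from about 2% at zero correlation to 8–25% at common correlations of 0.5 to 0.9 with equal adherence SDs. It is 6–10% at Sham correlations of 0.7 to 0.9 if the Hypoxia SD is halved. These rates depend on assumed correlations and SDs. The consequence is confined to the adherence claim.

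**What to change.** For each outcome, fit one regression of change on Group, adherence (centred at the overall mean) and Group × adherence to all participants. Report:

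- the slope difference (the product coefficient) with its 95% confidence interval;
- the Group difference at mean adherence with its 95% confidence interval. The parenthesis in the plan speaks of outcome change at equal adherence, which parallel lines with an offset would also satisfy.

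State that a slope difference is claimed only if its interval excludes zero, and that a larger estimate, or significance in one arm only, is not evidence of one. Name one adherence threshold for the main analysis before the data are seen, since the text leaves two open. Label the analysis exploratory, also because adherence is measured after randomization and the arms are not protected by it when compared at equal adherence. If a pooled model was already intended, this only writes it down.

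The cost is wording; no visits, data or participants are added. The downside is a wide interval on 4 residual df: with about 6–14% power for a 1.5-fold slope under the assumptions above, the prediction will usually be reported as unresolved.
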